3.5 Concomitant Medications, Treatments, and Procedures

Investigators may prescribe concomitant medications or treatments deemed necessary to provide supportive care except for prohibited medications (see Section 3.5.1). Best supportive care should be provided when necessary for all subjects (including antibiotics, bisphosphonates, receptor activator of nuclear factor kappa B ligand (RANKL) inhibitors, nutritional support, correction of metabolic disorders, optimal symptom control, and pain management including palliative radiotherapy after consultation with the Sponsor Medical Monitor.

Use of inhaled, topical, intranasal corticosteroids or local steroid injections (e.g., intra-articular injection) is permitted. Temporary use of corticosteroids (e.g., prior to computed tomography [CT] to prevent contrast allergies) is acceptable after consultation with the Sponsor Medical Monitor.

3.5.1 Prohibited Medications/Treatments

Subjects must be instructed not to take any medications, including over-the-counter products without first consulting with the investigator. The following medications are prohibited during SL-172154 therapy:

- Any investigational anti-cancer therapy not described in this protocol
- Any concurrent chemotherapy, radiotherapy (except palliative radiotherapy after consultation with the Sponsor Medical Monitor), hormonal or hormonal suppression therapy for anti-cancer intent, immunotherapy, or biologic therapy for cancer treatment
- Immunosuppressive medications for primary prophylaxis against IRRs are not permitted. Subjects who require immunosuppressive medications (e.g., corticosteroids) for management of irAEs or IRRs should be managed per Toxicity Management Guidelines in Section 3.6.
- Live attenuated vaccines during the study through 30 days after the last dose of SL-172154

3.5.2 Medications to be used with Caution

SL-172154 is a therapeutic protein that may induce the transient release of cytokines including IL-6 which in turn, may inhibit the activity of cytochrome P450 (CYP450) enzymes including CYP3A4 activity [Evers, 2013]. Although not tested clinically, a drug-drug interaction may occur with the coadministration of medications that are CYP450 substrates. Drugs metabolized by CYP450 enzymes may have reduced clearance or an increase in half-life or peak plasma concentration and should be used with caution. There may be an increased risk of side effects for drugs that are CYP450 substrates. Where possible consider substitutions for these medicinal products if therapeutic effects cannot be monitored.

A complete list of drugs that are CYP450 substrates including CYP3A4 substrates is available at: https://drug-interactions.medicine.iu.edu/Main-Table.aspx (Flockhart Table).

3.6 Toxicity Management Guidelines Dosing Delays/Dose Modifications

No dose reductions are permitted for SL-172154. The toxicity guidelines provided in this section represent general guidance for AEs that are considered by the investigator to be related to treatment with SL-172154. All AEs should be assessed using NCI-CTCAE v5.0 criteria. These guidelines are not meant to be prescriptive and investigators should always use clinical judgement in the determination of dosing. Investigators should always err on the side of caution if treatment-related toxicity is suspected. Subjects should be thoroughly evaluated to rule out any alternative etiology (e.g., disease progression, concomitant medications, and infections). In the absence of a clear alternative etiology, all events should be considered potentially immune related.

Please see Section 5.1.5 Monitoring Dose Administration for further information on SL-172154.

NOTE: Hereafter in this section and in subsequent sections, SL-172154 monotherapy may be referred to as SL-172154 or as IP.

Differentiating between IRRs that are due to either the common non-allergic hypersensitivity reactions [HSRs (e.g., CRS)] or the rarer allergic HSRs can be challenging due to overlapping clinical manifestations. There are no specific clinical features (including symptoms and timing of reaction) that can absolutely distinguish between these two entities. General guidance is provided below for IRRs secondary to both allergic and non-allergic HSRs e.g., CRS. These guidelines are not meant to be prescriptive. Established institutional guidelines should be followed where appropriate. At the resolution of the event, the entirety of the data including clinical symptoms, response to treatment and laboratory studies should be re-evaluated to determine the final etiology of the event. For purposes of standardized reporting, utilize terms based on best medical judgement of the AE/SAE and the definition found in NCI-CTCAE v5.0 for IRR, allergic reaction, anaphylaxis, and CRS.

Discretionary use of primary prophylaxis for IRR prevention for subjects enrolled at 3 mg/kg or less is permitted. However, as noted in Section 3.6.1, secondary prophylaxis (i.e., prevention of IRRs following an initial episode) for these subjects is appropriate and permitted at the discretion of the investigator for all dose levels. Primary prophylaxis for IRR prevention is required with each SL-172154 administration for subjects enrolled at 10mg/kg or higher dose levels. See Section 5.1.2.3 for details regarding the primary prophylaxis medications.

NOTE: In the event of a Grade ≥ 2 IRR, subjects will be observed on-site or hospitalized for close observation until resolution of symptoms as per Table 3.6.1.

ONFIDENTIAL	ompound: SL-172154
CO	Con

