3.3 SL-172154 Dose Escalation Plan

Dose escalation will begin on Schedule 1 at the starting dose of 0.1 milligrams per kilogram (mg/kg) as outlined in Table 1 below. Intermediate or higher dose levels not shown may be explored based on emerging data (e.g., safety and pharmacodynamic data). Dose escalation of SL-172154 will not exceed half-log increments. The DLT assessment period is 28 days in length and ends 14 days after the last dose is administered in the first cycle on Schedule 1 and 7 days after the last dose is administered on Schedule 2. Dose escalation will follow the mTPI-2 decision rules outlined in Table 7 in Section 9.1.

- Schedule 1 administration for SL-172154: Given on days 1, 8, and 15 in cycle 1 over 28 days and then every two weeks thereafter on days 1 and day 15 in cycles \geq 2 every 28 days.
- Schedule 2 administration for SL-172154: Given on days 1, 8, 15 and 22 of each 28-day cycle
- Cycle length for Schedules 1 and 2: 28 days
- **DLT assessment period for Schedules 1 and 2**: 28 days

Table 1: SL-172154 Dose Escalation Plan in Phase 1
--

	Dose LevelIV Dose of SL-172154 (mg/kg) ^{a,b,c,d,e} Duration of Infusion ^d				
Lev	evel 1 - starting dose 0.1 30 minutes (+/- 10 minutes)				
Lev	vel 2	0.3	30 minutes (+/- 10 minutes)		
Lev	vel 3	1.0	30 minutes(+/- 10 minutes)		
Level 4 3.0 60 minutes (+/- 15 minutes)					
Level 5 10.0 60 minutes (+/- 15 minutes)					
a) b)	cycle 1 and then on days Dose escalation on Sched once weekly on days 1, 8	1 and 15 in cycles \geq 2. Jule 2 may be tested: If Schedule 2 is of , 15, and 22 of each 28-day cycle.	in 28-day cycles on days 1, 8, and 15 in pened, SL-172154 may be administered		
c) d)	kg. For subjects with body weight >100 kg, the dose to be administered should be the same as that calculated for a subject weighing 100 kg (see Section $5.1.4$).				
e)	Infusion time may change based on final drug volume needed for administration, safety and tolerability of the infusion for the subject and/or observed safety findings during the study. Please refer to the Study				

Pharmacy Manual (SPM) for details.

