3.3.1 Intrasubject Dose Escalation

Intrasubject dose escalation(s) may be considered on a case-by-case basis, provided that the subject has completed at least 2 cycles at the originally assigned dose, has tolerated treatment well, and experienced \leq Grade 1 toxicity on the most recent cycle of SL-172154 therapy. A subject's dose may be increased to a dose level that has completed evaluation for safety and has not exceeded the MTD. Approval for intrasubject dose escalation must be obtained from the Sponsor Medical Monitor and must be documented on an Intrasubject Dose Escalation Decision Form provided by the Sponsor.

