5.1.2.3 Administration

Doses of SL-172154 are to be administered as an IV infusion via an infusion pump or syringe pump that can ensure precision within at least 0.1 mL/min. DO NOT USE an in-line filter for administration of SL-172154.

Premedication for IRR prophylaxis is required with each 10mg/kg or higher dose and is at the investigator's discretion for doses less than 10mg/kg. The following premedication is to be administered approximately 30 minutes prior to the start of each SL-172154 administration:

- acetaminophen (650 to 1000 mg PO)
- diphenhydramine (25-50 mg, or equivalent, PO or IV)
- ranitidine (50 mg IV or equivalent).

Infusion rate: The duration of infusion stipulated for each dose is outlined in Table 1: SL-172154 Dose Escalation Plan in Section 3.3.

NOTE: A physician must be present at the site or immediately available to respond to emergencies during all administrations of IP. A fully functional resuscitation facility must be available. IP must not be administered via IV push or bolus but as an IV infusion using an infusion or syringe pump.

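### Protocol Section 3.6 ties mandatory infusion-reaction premedication to the dose at which a subject enrolled and Section 5.1.2.3 to the dose given, so they differ for a subject later escalated to 10 mg/kg

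*Protocol*

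**What the plan says.** Two sections of the Protocol say when primary IRR prophylaxis is needed.

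- **Section 3.6** goes by enrolment dose. For lower doses: "Discretionary use of primary prophylaxis for IRR prevention for subjects enrolled at 3 mg/kg or less is permitted". For higher doses: "Primary prophylaxis for IRR prevention is required with each SL-172154 administration for subjects enrolled at 10mg/kg or higher dose levels". It then refers to Section 5.1.2.3 for the medications, without saying that 5.1.2.3 decides when they are required. It allows secondary prophylaxis, after a first reaction, at every dose level.
- **Section 5.1.2.3** goes by the dose given: "Premedication for IRR prophylaxis is required with each 10mg/kg or higher dose", and it is at the investigator's "discretion for doses less than 10mg/kg".

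Enrolled dose and given dose can differ. Under Section 3.3.1 a subject's "dose may be increased to a dose level that has completed evaluation for safety and has not exceeded the MTD", provided that "the subject has completed at least 2 cycles at the originally assigned dose", treatment was well tolerated and toxicity in the latest cycle was no worse than Grade 1. It adds: "Approval for intrasubject dose escalation must be obtained from the Sponsor Medical Monitor". Section 3.6 rules out dose reductions, so the two doses can differ only by an upward move.

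The planned levels in Table 1 are 0.1, 0.3, 1, 3 and 10 mg/kg. Section 3.3 adds: "Intermediate or higher dose levels not shown may be explored based on emerging data".

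**The concern.** One safety instruction is given with two different triggers. While a subject stays at the enrolled level, both sections give the same answer on the planned doses. After escalation to 10 mg/kg they do not: a site working from 3.6 could treat premedication as optional at an infusion where 5.1.2.3 makes it mandatory.

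The infusion concerned is one where a clear rule is useful:

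- Section 1.4.1 names IRRs and cytokine release as potential human risks. In the monkey GLP study (Section 1.2.4) the reactions were dose-dependent and seen at 10 and 40 mg/kg. Section 3.2 places the toxicity at the third and later doses.
- Scheduled vital signs are lighter by then. Under footnote d of the schedules in Sections 6.1 and 6.2, they run to 6 hours after the start of infusion on Cycle 1 dosing days and on most Cycle 2 dosing days. From Cycle 3 Day 1 they are taken only before the dose and at the end of infusion. Section 5.1.5 still requires monitoring during and after every infusion.
- Section 14.4 counts any departure from the protocol as a deviation. Omitting premedication at an escalated 10 mg/kg infusion would be a deviation under 5.1.2.3 and not under 3.6.
- The Grade 1 row of the IRR table in Section 3.6.1 depends on whether premedication is already mandatory, so it inherits both answers.

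**Working it through.** The plan gives no figure to reproduce. The check applies both rules to every possible pair of enrolled and given dose.

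**Inputs.** Five levels from Table 1; upward moves only (3.6); premedication rules from 3.6 and 5.1.2.3; 28-day cycles and a 28-day DLT period (3.3); at least two completed cycles before escalation (3.3.1).

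**Number of pairs.** Unchanged dose: 5. Upward moves: C(5,2) = 10. Total: 5 + 10 = 15.

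| Enrolled (mg/kg) | Given (mg/kg) | Pairs | Section 3.6 | Section 5.1.2.3 | Same? |
|---|---|---|---|---|---|
| 3 or less | 3 or less | 4 unchanged + C(4,2) = 6 upward = 10 | discretionary | discretionary | yes |
| 10 | 10 | 1 | required | required | yes |
| 0.1, 0.3, 1 or 3 | 10 | 4 | discretionary | required | **no** |

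The sections agree on 10 + 1 = 11 pairs and disagree on 4.

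**Intermediate level between 3 and 10 mg/kg, if opened.** At that level 3.6 is silent on primary prophylaxis and 5.1.2.3 makes it discretionary. After escalation from there to 10 mg/kg, 3.6 is still silent and 5.1.2.3 requires it.

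**Earliest possible affected infusion.** Two completed cycles take 2 × 28 = 56 days, so the first opportunity is Day 57 (Cycle 3 Day 1). That is 57 − 28 = 29 days after the last day of the DLT period. Planned doses before it: Schedule 1, 3 + 2 = 5; Schedule 2, 4 + 4 = 8.

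Day 57 is a lower bound, because 10 mg/kg must itself have been cleared for safety. A subject in the first 0.1 mg/kg escalation cohort must wait for four further levels, at least 4 × 28 = 112 days beyond the 28-day period at 0.1 mg/kg, or 140 days in all. Day 57 can apply only to someone enrolled late enough at a lower level, for example in a pharmacodynamic or expansion cohort opened below 10 mg/kg after 10 mg/kg was cleared.

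**After the fix.** Both rules depend on the given dose with one cut-point at 10 mg/kg, so 0 of 15 pairs differ, and any intermediate or higher level gets the same answer in both sections.

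**The case against.** The best reply is that no infusion lacks an instruction. Section 5.1.2.3 is the administration section and covers every dose given, after escalation or at an intermediate level. The stated rationale for Amendment 05 places the premedication instructions in Section 5, whereas 3.6 calls its own content general and non-prescriptive. The rules can also be followed together: 3.6 only permits discretion, so premedicating at 10 mg/kg complies with both. Escalation needs Medical Monitor approval and good recent tolerance, and 5.1.2.3 requires a physician and resuscitation facilities to be available. The March and June 2022 clarification memos cited under Table 1 of the SAP changed infusion durations at 10 and 3 mg/kg; whether they or the Pharmacy Manual also addressed premedication cannot be seen here.

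Most of this stands, and it keeps the point small. It does not remove it. The cross-reference in 3.6 covers the medications and not the trigger, and nothing in the protocol says that 5.1.2.3 prevails. Section 3.6 still permits an omission that 5.1.2.3 forbids.

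Readers might also infer more than the text supports:

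- *That the protocol has no rule between 3 and 10 mg/kg.* It has one: 5.1.2.3 makes those doses discretionary. Only 3.6 is silent, and no planned level lies in that range.
- *That DLT counts or the MTD are affected.* Protocol Section 9.2.4 and SAP Section 8.1 use only DLTs in the DLT period at the initial dose, and escalation cannot come before Day 57.
- *That subjects went without premedication or that IRR rates changed.* The documents do not say how many subjects escalated, if any, or what they received.
- *That all four discordant pairs arise at Day 57 in one step.* Clearance of 10 mg/kg must come first. If the half-log limit in Section 3.3 also binds within subjects, only 3 to 10 mg/kg is a single step; the other three would need successive steps, which the wording of 3.3.1 appears to allow.

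**Conclusion.** The inconsistency is real and narrow. For a subject enrolled below 10 mg/kg and escalated to 10 mg/kg, 3.6 does not require premedication (it is expressly discretionary if enrolment was at 3 mg/kg or less) and 5.1.2.3 does. The 4 discordant combinations out of 15 describe the wording and do not estimate the subjects or infusions affected.

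The conclusion assumes that enrolment dose in 3.6 means the originally assigned level, and that 10 mg/kg is cleared and not above the MTD. If 10 mg/kg is never cleared, no planned combination is affected. The practical risk is small and no analysis changes. It is worth correcting because it is a patient-safety instruction and the two versions classify the same omission differently.

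**What to change.** Change two phrases in Section 3.6 so that it follows the dose received, as 5.1.2.3 does:

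- In the sentence that makes prophylaxis mandatory, replace the reference to enrolment at 10 mg/kg or higher with *subjects receiving 10 mg/kg or higher, including after intrasubject escalation*.
- In the sentence that makes it discretionary, replace the reference to enrolment at 3 mg/kg or less with *receiving less than 10 mg/kg*.

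This also removes the silence in 3.6 between 3 and 10 mg/kg and settles the Grade 1 row in 3.6.1. Section 5.1.2.3, the drugs, the visits, the data collected and the analyses stay as they are. The cost is two phrases in the next amendment or in a clarification memo, a route the sponsor has already used for infusion duration at 3 and 10 mg/kg.

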		 Temporarily interrupt SL-172154 or decrease the rate of the infusion by 50%. Begin IV infusion of normal saline and treat with antipyretics, histamine 1 and 2 (H1 and H2) antihistamines, and leukotriene inhibitor. Conticosteroids and/or bronchodilator therapy may also be administered as appropriate. Consider opioids (e.g., meperidine) for rigors. Monitor subjects with close observation in an outpatient or inpatient setting for a minimum of 12 hours or until recovery from symptoms. Consider daministened admission to hospital.
	Grade 2	 If the infusion is interrupted, then restart the infusion at no more than 50% of the rate at which the reaction symptoms occurred. For subsequent infusions, consider starting infusion at 50% rate at which the symptoms occurred and titrate to tolerance. If symptoms recur, then no further SL-172154 will be administered at this visit. The following prophylactic pre-medications are recommended for future infusions: antipyretics, antihistamines with/without corticosteroids per institutional guidelines
	-	 Immediately discontinue infusion of SL-172154 Begin IV infusion of normal saline and treat with epinephrine, bronchodilators, diphenhydramine, ranitidine, corticosteroids, oxygen, fluids, vasopressors, etc. and consider opioids (e.g., meperidine) for rigors. as indicated and per institutional guidelines. Epinephrine is the drug of choice in an anaphylactic reaction and its administration should not be delayed. Monitor subjects with close observation in an outpatient or inpatient setting for a minimum of 12 hours or until recovery from symptoms. Consider daministration and in an outpatient or inpatient setting for a minimum of 12 hours or until recovery from symptoms. Consider admission to hospital.
	Grade 3	 Rechallenge should not be attempted in cases of true anaphylaxis. In other cases, once subject has completely recovered, carefully consider if it is safe for the subject to receive SL-172154 at the next scheduled dose with pre-medication (e.g., corticosteroids, antihistamines, antipyretics) and slow infusion (≤ 50% of the rate at which the reaction occurred). The next two subsequent infusions of SL-172154 (after an event of grade 3 event of infusion-related reaction) must be administered in an inpatient or outpatient setting with prolonged observation for a minimum of 12 hours after the completion of the infusion. Start infusion at 50% rate at which the symptoms occurred. If no further symptoms, rate may be escalated at intervals and increments as clinically appropriate. If symptoms recur, permanently discontinue SL-172154.

IDENTIAL	ound: SL-172154
CONFIDEN	Compound

Instance Eventuating to hospital for does observation until resolution of symptoms. hypersensitivity Crade 4 Admit to hospital for does observation until resolution of symptoms. reactions Manage sevee RRsp per instruments standard (e.g., apreprintine, applientlydramine, randidine, corfroosteroids, bronchodilators, oxygen, or and oxnister poiolds (e.g., meperidine) for rigors. Epinephrine, applientlydramine, randidine, corfroosteroids, bronchodilators, oxygen, previous page) Adverse Event Grade 4 Namage sevee RRsp per instruments, applications, displayed immune activation with concomilant elevations of cytokine rescion and its administration or to be alloyed Adverse Event Cremeral Cuidiance for Cytokine Release Syndrome (CRS) (Rosello, 2017; Porter, 2018) Adverse Event Cremeral and systemic inflammation stated course as the otory of optice in an anaphylactic reaction and its administration or to perform expression. Barkyprost attrastaming stated course include (but are not confined to) fewer, fluckles symptoms, rash, nauses, vorning, darther progress to life threatening capility indistinguishable. Specify Management Amangement Amangement Amangement Crade 1 Management Management Amangement Amangement Amangement Syndrome co Grade 1 Management Amangement Amangement Amangement Cradet adversage pressing the ra		Severity (Symptoms)	Management
Telease It	Infusion or hypersensitivity reactions (continued from previous page)	Grade 4	 Permanently discontinue SL-172154. Admit to hospital for close observation until resolution of symptoms Manage severe IRRs per institutional standards (e.g., epinephrine, diphenhydramine, ranitidine, corticosteroids, bronchodilators, oxygen, fluids, etc. and consider opioids (e.g., meperidine) for rigors. Epinephrine is the drug of choice in an anaphylactic reaction and its administration should not be delayed
release	Adverse Event	General G	uidance for Cytokine Release Syndrome (CRS) [Rosello, 2017; Porter, 2018]
Subjects with extensive comorbidities or those of older age should be treated as for Grade 3. Subjects with worsening symptom of the second sector Grade 3.	Cytokine-release Syndrome	CRS is a non- IL-6, IL-10, Tr hypotension, progress to life to a type 1 HS Severity (symptoms) Grade 1 Grade 2	 CRS is a non-artigen specific, systemic inflarmatory response that occurs as result of high-level immune activation with concomitant elevations of cytokines (e.g., IL-10, TWF-o, IL-2, IFNY). Clineal returnes of the syndrome include (but are not confined to) lever, ill-view symbolis, hypothersion, and the syndrome include (but are not confined to) lever, ill-view and polarise, anothing, hypothersion, and partient, neurologic manifestations. The syndrome can progress to life-threatening capillary leak, hypoxic respiratory failure, vasoditatory shock and end-organ dystunction. NOTE: CRS may have a similar presentation to a type 1 HSR and may be clinically indistinguishable. Severity Management Consider decreasing the rate of the infusion of SL-172154 by 50%, until resolution of the event Monitor subjects with close observation in an outpatient setting for a minimum of 12 hours or until recovery from symptoms. Grade 1 Monitor subjects with close observation in an outpatient setting for a minimum of 12 hours or until recovery from symptoms. Grade 1 Monitor subjects with close observation in an outpatient setting for a minimum of 12 hours or until recovery from symptoms. Grade 1 Monitor subjects with close observation in an outpatient setting for a minimum of 12 hours or until recovery from symptoms. Grade 1 Monitor subjects with close observation in an outpatient setting for a minimum of 12 hours or until recovery from symptoms. Grade 1 For subsequent indusions, consider provingent (e.g., antipyretics, anthistamines) per institutional guidelines For subsequent indusions of SL-172154 (per equivalent does of corticosterioid every 6 hours and manage per institutional guidelines. Consider and second on 6 symptoms. Grade 2 Monitor subjects with close observation in an outpatient of grade 2 CRS) must be administrated in an inpatient or outpatient setting with prolonged observation

CONFIDENTIAL	Compound: SL-172154
00	Co

Adverse Event	Severity (Symptoms)	Management
		 Interrupt SL-172154 Hospitalization required for management of symptoms related to organ dysfunction: admit to the hospital and potentially the intensive care unit
Cytokine-release		or equivalent for close monitoring and management
Syndrome		• Treat hypotension with IV fluid for blood pressure support and/or pressers. Administer oxygen for treatment of hypoxia. Cryoprecipitate or fresh
(continued from		frozen plasma may be required for coagulopathy. Manage per institutional guidelines.
previous page)		Manage severe IRRs and CRS per institutional standards (e.g., epinephrine, diphenhydramine, ranitidine, corticosteroids, bronchodilators,
		oxygen, fluids, meperidine for rigors, etc.). Epinephrine is the drug of choice in an anaphylactic reaction and its administration should not be delayed
		 Administer tocilizumab at a dose of 8 mg/kg. If clinical improvement does not occur within 24 hours, administer a second dose of tocilizumab.
		 Second-line therapies:
	Grade 3 or 4	dexamethasone
		 anti-TNF-α mAbs (infliximab) or soluble TNF-α receptor (etanercept), or IL-1R-based inhibitors (anakinra).
		 For Grade 3 CRS, may consider rechallenge after consultation with medical monitor. If rechallenge is given:
		 The next two subsequent infusions of SL-172154 (after an event of grade 2 CRS) must be administered in an inpatient or outpatient
		setting with prolonged observation for a minimum of 12 hours after the completion of the infusion.
		 Start infusion at 50% rate at which the symptoms occurred. If no further symptoms, rate may be escalated at intervals and increments
		as clinically appropriate.
		 After a Grade 3 CRS event, subjects must be premedicated with high dose steroids prior to the next infusion of SL-172154.
		 If there is no evidence of CRS with the subsequent infusion, premedication with high dose steroids may be omitted for subsequent
		infusions.
		 Any patient that experiences recurrence of Grade 3 CRS following re-treatment must be permanently discontinued from study
		treatment.
		 For Grade 4 CRS, permanently discontinue SL-172154.

NFIDENTIAL	mpound: SL-172154
CON	Comp

